BACKGROUND AND RATIONALE:

AL amyloidosis is a variant plasma cell disorder in which clonal bone marrow plasma cells produce immunoglobulin light chains that misfold into fibrils that are deposited in visceral organs, leading to organ dysfunction and failure. Untreated, the disease has a median survival of only about one year. Oral treatment with melphalan and dexamethasone produces improvement in survival, with hematologic remissions and improvement in organ function. Aggressive treatment with high dose intravenous melphalan with autologous stem cell transplantation (HDM/SCT) produces complete hematologic responses (CR) in about 40% of subjects and partial responses in a similar proportion; these are frequently accompanied by stabilization or improvement in organ function. Unfortunately only about half of referred subjects are eligible for HDM/SCT. Furthermore, it has been observed by us as well as other groups that achievement of a hematologic complete response after treatment with oral melphalan and dexamethasone as well as HDM/SCT is associated with improved survival, QOL, and clinical/organ response. Thus, we continue to seek more effective regimens for subjects ineligible for aggressive treatment with HDM/SCT or not achieving a complete hematologic response to HDM/SCT or other modalities.

The advent of novel agents in the treatment of multiple myeloma has changed the therapeutic landscape of plasma cell dyscrasias. Thalidomide has been studied as a single agent and in combination with dexamethasone for the treatment of AL amyloidosis. Unfortunately, thalidomide is poorly tolerated with 50-65% of subjects experiencing grade 3 and 4 toxicities, leading to drug withdrawal in approximately half of the subjects.

We are concluding a phase II study of lenalidomide alone and in combination with dexamethasone for subjects with AL amyloidosis. This study included untreated as well as relapsed subjects after HDM/SCT. Interim analysis of the first 34 subjects suggests achievement of a complete hematologic response CR in ~30% subjects and of partial

hematologic response in ~40% subjects, with most responses occurring with the lenalidomide/dexamethasone combination. A variety of toxicities have been observed, including leukopenia, rash, venous thrombosis, and intolerance to the dexamethasone. This report indicated better tolerability than thalidomide, however, 20% of subjects still stopped treatment with lenalidomide due to toxicities. We have extended our study to subjects on dialysis, using attenuated doses, with good preliminary results. A study using lenalidomide in combination with melphalan and dexamethasone is ongoing; this study is not suitable for subjects with significant prior exposure to alkylator agent.

Pomalidomide (CC4047), a 2nd generation immune-modulatory drug, has shown promising activity in phase-2 trial in combination with low-dose dexamethasone for relapsed or refractory multiple myeloma and AL amyloidosis. Responses were seen in 50% of subjects previously-failing thalidomide and/or lenalidomide in AL amyloidosis.

Given these promising results of pomalidomide in plasma cell dyscrasias, we propose a study of pomalidomide and low dose dexamethasone in persons with previously-treated AL amyloidosis.

STUDY OBJECTIVES:

Primary:

• Determine dose-limiting toxicity (DLT) and the maximum tolerated dose (MTD) of pomalidomide combined with dexamethasone in persons with previously-treated light-chain (AL)-amyloidosis.

Secondary:

- Determine the following at the MTD:
 - Hematological complete (CR) very good partial (VGPR) and partial (PR) rates
 - Response-duration
 - Organ response
 - Time-to-event
 - Survival

Exploratory:

• To investigate the relationship of changes in the levels of the biomarkers BNP and troponin I to frequency of specific adverse events and the occurrence of DLT.

STUDY DESIGN:

Phase-I/II dose-escalation study of pomalidomide and dexamethasone in persons with previously-treated AL-amyloidosis. During the Phase I portion the MTD will be determined based on DLTs in the first cycle. At the MTD an expanded cohort of 12 subjects will be evaluated to estimate efficacy.

The study includes a screening period, a treatment (dose escalation) period, and a follow-up period for survival. After giving written informed consent, subjects will be evaluated for eligibility for enrollment in the study and baseline evaluations will be performed. Subjects who satisfy all inclusion and exclusion criteria will begin study drug treatment with dose escalation. Standard dose escalation rules will be used.

Subjects will be monitored every cycle for safety, hematological status, and organ function during therapy or until the occurrence of progressive disease (PD).

Treatment Group Assignments and Subject Replacement

This is a dose-escalation study and dose escalation will proceed through 3 dose-levels according to standard rules in which dose levels are started sequentially after complete evaluation of the occurrence of DLT. Based on the dose escalation scheme, as many as 30 subjects could be enrolled in the study. Subjects who discontinue pomalidomide for reasons other than DLT before completing at least 2 treatment cycles are to be replaced.

Subpopulations

An additional 12 subjects will be enrolled in an expanded cohort for analysis of efficacy at each schedule studied.

Subjects in this cohort will be treated at the dose defined as the MTD for that schedule.

Schema:

Phase-I:

Pomalidomide 2 mg/day D1-21 – dose escalation to 4 mg/day by 1 mg units* Dexamethasone 10-20 mg D1, 8, 15, 22

* Pomalidomide dosing for Phase I cohorts 1 and 2 given on days 1-28 of a 28-day cycle and changed to Days 1-21 of a 28 day cycle with Cohort 3.

This cycle will be repeated every 28 days.

Subjects will take aspirin 325 mg/day to prevent venous thrombosis whilst on-study. A proton pump inhibitor will be used for GI prophylaxis.

Phase-II:

Pomalidomide [MTD] mg/day D1-21 Dexamethasone 10-20 mg D1, 8, 15, 22

This cycle will be repeated every 28 days.

Subjects will take aspirin 325 mg/day for prophylaxis against venous thrombosis while on study.

A proton pump inhibitor will be used for GI prophylaxis.

STUDY ENDPOINTS

Primary:

• Dose-limiting toxicity (DLT) and maximum tolerated dose (MTD) of pomalidomide in combination with dexamethasone

Secondary:

To be determined for MTD:

- Hematological complete (CR) very good partial (VGPR) and partial (PR) rates
- Response-duration
- Organ response
- Time-to-event
- Survival

Exploratory:

• relationship of changes in the levels of the biomarkers BNP and troponin I compared to frequency of specific adverse events and the occurrence of DLT

STUDY DURATION: Treatment may continue until subject experiences unacceptable toxicities or disease progression. Follow-up will take place every 3 months until disease progression, then annually for survival. Accrual ~24 months	TOTAL SAMPLE SIZE: 30 subjects
DOSING REGIMEN(S):	STUDY DRUG SUPPLIES:
Phase I portion:	Celgene Corporation will
Pomalidomide 2 mg/day D1-21 – dose escalation to 4 mg/day in 1 mg increments in phase I* Dexamethasone 10-20 mg D1, 8, 15, 22 The above cycle will be repeated every 28 days. * Pomalidomide dosing for Phase I cohorts 1 and 2 given on days 1- 28 of a 28-day cycle and changed to Days 1-21 of a 28 day cycle with Cohort 3.	supply pomalidomide as 1.0 mg and 2.0 mg
Phase II portion:	
Pomalidomide [MTD] mg/day D1-28 Dexamethasone 10-20 mg D1, 8, 15, 22	
This cycle will be repeated every 28 days.	

Protocol

2 Schedule of Study Assessments *

Pre-Study Cycle One*		Cycle One*			Cycles 2, 3	Cycles* 5, 6, 8, 9, 11, 12	Cycles* 4, 7 and 10 ∞	*30 days of discontinuation From Study Drug	Follow-Up ⁸ Phase	
		Day 1	Day 8 §	Day 15	Day 22 §	Day 1	Day 1	Day 1		Every 3 months
Physical examination, vital signs, weight	х	х			х	Х		Х	х	х
SWOG performance status	Х	Х			Х	Х		Х	Х	Х
CBC with differential	Х	Х	X ⁶	X ⁶	X ⁶	X ⁶	X ⁶	Х		Х
Pregnancy test ²	X ^{2, 3}	X ³	X ³	X ³	X ³	X ³	X ³	X ³	X ³	
Education and counseling guidance ⁷		X 7				X ⁷	X ⁷	X ⁷		
Sodium, chloride, CO2, Glucose	Х	Х	х	х	х	Х	х			х
BUN, creatinine, potassium, Magnesium, phosphorous	х	х	х	х	х	х	х	х		х
ALT, AST, albumin, alk phos, bilirubin	х	х				Х	x			х
calcium	Х	Х				Х	Х	Х		Х
Cholesterol, triglyceride, TSH	х							Х		х
Total Protein, LDH, INR, PTT	x	х						Х		х
BNP, uric acid	Х	Х	Х	Х	Х	Х	Х	Х		Х
C-reactive protein, Beta 2- microglobulin	х							Х		х
IgG, IgA, IgM	Х							Х		Х
Serum immunofixation electrophoresis	x							Х		х
Urine immunofixation electrophoresis	х							Х		х
24 hour urine protein	Х							Х		Х
Free light chain assay	Х					Х	Х	Х		Х
Bone marrow biopsy and aspirate	х							X ⁵		X ⁵
EKG	Х							Х		Х
ECHO	Х							X ⁵		X ⁵
CXR	Х							X ⁵		X ⁵
Urinalysis	Х							Х		Х

Dispensement of Cycle 1		V								
study drug		^								
Record adverse events			Х	Х	Х	Х	Х	Х	Х	
Record concomitant therapies/procedures		х				Х	Х	Х	х	
Dispense study drug for next cycle		х				х	Х	Х		
Perform drug accountability		х				х	Х	Х	х	

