5.4 Drug Administration

5.4.1 Treatment assignments

The Phase I portion of the study will be aimed at determining the safety profile and the MTD of Pomalidomide. A 3+3 dose escalation scheme will be implemented. Subjects will receive escalating doses of Pomalidomide orally on D1-21 in a 28-day cycle* in the absence of disease progression or unacceptable toxicity. DLTs will be assessed in Cycle 1 only. Dose escalation of Pomalidomide will continue until MTD has been identified or a maximum planned dose (4 mg/day D1-21) is determined to be safe.

* Pomalidomide dosing for Phase I cohorts 1 and 2 given on days 1-28 of a 28-day cycle and changed to Days 1-21 of a 28 day cycle with Cohort 3.

The Phase II portion of the study will begin after determination of the MTD and evaluation of the safety profile at the MTD in at least 6 subjects. The dose for administration will be informed by the results of the Phase I portion of the study. In the Phase II, eligible subjects will receive Pomalidomide at the MTD or the maximum planned dose from D1-21.

Once the MTD is defined during Phase I, patients currently receiving treatment may discuss the option with the treating investigator to continue on their current dose, or increase to the MTD, if they have not achieved a complete response.

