5.5.2 Dose-Reduction Steps

Dose-reduction steps are below:

Table 1: Pomalidomide Dose Reduction Steps for Phase I and II				
Starting Dose	MTD (as determined in Phase I portion) mg daily on Days 1-28 every 28 days			
Dose Level – 1	Decrease by 1 mg daily from MTD on Days 1-21 every 28 days*			
Dose Level – 2	Decrease by 2 mg daily from MTD on Days 1-21 every 28 days*			
Dose Level – 3	Decrease by 3 mg daily from MTD on Days 1-21 every 28 days*			

* Pomalidomide dosing for Phase I cohorts 1 and 2 given on days 1-28 of a 28-day cycle and changed to Days 1-21 of a 28 day cycle with Cohort 3.

Table 2: DEXAMETHASONE Dose Reduction Steps for Phase I and II		
Starting Dose 20 mg QD once weekly every 28 days		
Dose Level –1	10 mg QD once weekly every 28 days	
Dose Level –2	4 mg QD once weekly every 28 days	

Pomalidomide	Page 27 of 66 Protocol:

Dosing will be adjusted as needed by study investigators as outlined in the tables in Section 5.5.3. If dexamethasone is permanently discontinued, the patient will continue with single agent Pomalidomide.

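### Phase II pomalidomide is written as days 1-21 in some places and days 1-28 in others; at 4 mg the longer schedule would exceed every tested cohort's dose per cycle by a third

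*Combined protocol and SAP*

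**What the plan says.** Days 1-21 for Phase II:
- The synopsis schema and the Section 5.1 schema both read "Pomalidomide [MTD] mg/day D1-21".
- Section 5.4.1: "In the Phase II, eligible subjects will receive Pomalidomide at the MTD or the maximum planned dose from D1-21".

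Days 1-28 for Phase II:
- Synopsis, Dosing regimen(s) box, Phase II portion: "Pomalidomide [MTD] mg/day D1-28".
- Section 5.5.2, Table 1, which is headed for both phases. The starting dose is "MTD (as determined in Phase I portion) mg daily on Days 1-28 every 28 days", while the first reduction step is "Decrease by 1 mg daily from MTD on Days 1-21 every 28 days".

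The ceiling for escalation also differs. Section 5.4.1 continues escalation until an MTD is found or "a maximum planned dose (4 mg/day D1-21) is determined to be safe". Section 10.1 gives the same 4 mg ceiling as continuous dosing.

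A repeated footnote says that Phase I cohorts 1 and 2 (2 and 3 mg) were dosed on days 1-28 and that the change to days 1-21 came with cohort 3 (4 mg). The 3+3 rule in Section 5.4.2 and the MTD definition in Sections 5.4.2 and 10.2 name a dose level and no schedule. The Subpopulations paragraphs (synopsis and Section 5.1) and footnote a of Table 15-1 do refer to an MTD specific to a schedule. Section 5.4.1 adds that, once the MTD is known, "patients currently receiving treatment may discuss the option with the treating investigator to continue on their current dose, or increase to the MTD", provided they have not reached a complete response. It does not say which schedule they then follow.

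**The concern.** The synopsis box and Table 1 are places from which a site may dose, and they disagree with the treatment section. The footnote does not reconcile them. It covers Phase I cohorts only, and in Table 1 its asterisk sits on the reduction rows, not on the starting dose.

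The stake is exposure that Phase I did not test. Section 5.4.1 requires "evaluation of the safety profile at the MTD in at least 6 subjects" before Phase II starts. If the MTD is 4 mg, those subjects will have been treated on days 1-21, and no starting cohort will have received 4 mg on days 22-28. Sections 3.2 and 5.1.1.3 report a daily-dosing MTD of 2 mg in myeloma, with neutropenia the main dose-limiting toxicity at higher doses, so a fourth week at 4 mg is not a trivial addition.

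The second stake is the primary endpoint. One escalation sequence switches schedule between its second and third dose levels, so an MTD given in milligrams alone does not fully describe the regimen that was cleared.

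**Working it through.** **Plan's own total.** Section 10.3 allows three cohorts of up to 6 plus an expansion of 12: 3 x 6 + 12 = 30, as stated. The total therefore pays for one expansion, not one for each of two schedules.

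**Dose per 28-day cycle** = daily dose x dosing days. Daily doses are from Table 15-1 and dosing days from the cohort footnote.

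| Regimen | Calculation | mg per cycle | Tested as a Phase I starting regimen? |
|---|---|---|---|
| Cohort 1: 2 mg, days 1-28 | 2 x 28 | 56 | yes |
| Cohort 2: 3 mg, days 1-28 | 3 x 28 | 84 | yes |
| Cohort 3: 4 mg, days 1-21 | 4 x 21 | 84 | yes |
| 4 mg, days 1-28 (synopsis box or Table 1) | 4 x 28 | 112 | no |
| 3 mg, days 1-21 (if cohort 3 fails) | 3 x 21 | 63 | no, but lower than cohort 2 |

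**Excess if 4 mg clears and a day 1-28 line is followed.** 112/84 - 1 = 33.3% above the highest tested cohort.

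**Where the excess does not arise.** If the MTD is 3 mg or 2 mg, days 1-28 gives 84 or 56 mg, which are the cohort 2 and cohort 1 regimens. The exposure problem is confined to an MTD of 4 mg.

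**Who could be affected at 4 mg.** Up to 12 Phase II subjects. Also any cohort 1 or 2 subject who is still on treatment, is not in complete response, chooses to increase, and keeps days 1-28. When cohort 3 opens, those two cohorts hold 3 to 6 evaluable subjects each, so 6 to 12 in all; the number who would meet every condition is unknown.

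**If cohort 3 fails.** The rule returns to the previous dose, 3 mg, cleared on days 1-28, while Section 5.4.1 gives Phase II on days 1-21. 63/84 - 1 = -25%, so exposure falls.

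**The case against.** The best reply is that the intended schedule is clear. The detailed treatment section and both schemas agree on days 1-21, and the day 1-28 lines look like wording that survived the schedule change. That is probably right, and it limits the point to an internal contradiction with an easy correction. It does not remove it, because nothing in the document says which text prevails.

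The reply also stands against several stronger readings that a reader might infer:

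- *That nothing ties the MTD to a schedule.* Not so. The Subpopulations paragraphs and Table 15-1 footnote a do. Only the formal definition and the 3+3 rule omit it, and no rule says how a schedule-specific MTD is to be set.
- *That the fallback to 3 mg is a toxicity risk.* It lowers exposure by 25%. Accepting a daily dose cleared on the longer schedule for the shorter one is conservative; the plan only needs to say so.
- *That efficacy estimates would mix schedules.* Section 10.3 names the 12 expansion subjects as the efficacy population, and under Section 5.4.1 all 12 are on days 1-21. The set of 18 appears there in a precision illustration with hypothetical data.
- *That Section 10.1 prescribes an untested Phase II dose.* Its continuous 4 mg is a Phase I ceiling and conflicts with that section's own day 1-21 text and footnote. It needs a wording correction.
- *That Table 3 settles the schedule.* Its restart window, which closes at day 21, fits either schedule and is evidence for neither.

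The dose-increase route is the weaker of the two routes to 112 mg. It needs several conditions at once, and Section 5.4.1 itself gives the 4 mg ceiling on days 1-21. One clarifying clause is enough.

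**Conclusion.** The contradiction is real and should be fixed. Phase II dosing is days 1-21 in three places and days 1-28 in two, all in current text. Its size is 112 against 84 mg per cycle, 33% above the highest tested cohort, for up to 12 Phase II subjects and possibly some who continue from cohorts 1 and 2. This rests on two conditions: that 4 mg clears in cohort 3, and that someone doses from a day 1-28 line or leaves an escalated subject on days 1-28. It also takes milligrams per cycle as the measure of exposure.

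Separately, the formal MTD definition omits the schedule although the escalation changes schedule part-way. That is a gap in defining the primary endpoint, not an added risk. The documents do not show that Phase II was meant to run on days 1-28, or that any subject was dosed that way.

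**What to change.** 1. Change the Phase II line of the synopsis dosing box and the starting-dose row of Table 1 to days 1-21. Change the Section 10.1 ceiling to 4 mg/day on days 1-21.
2. State in Section 5.4.1 that a subject who increases to the MTD also moves to days 1-21.
3. Define the MTD in Sections 5.4.2 and 10.2 as a dose together with its schedule. Add one sentence saying that, if cohort 3 fails, 3 mg cleared on days 1-28 is accepted for use on days 1-21.
4. Replace the per-schedule wording in the Subpopulations paragraphs (synopsis and Section 5.1), Table 15-1 footnote a and Section 10.3 with a single expansion of 12 at the MTD on days 1-21. In the Subpopulations paragraphs, edit both sentences, so that no reference to an MTD for an unnamed schedule remains.

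The cost is a wording amendment. No subjects are added, and the maximum of 30 is unchanged.

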
3 Background and Rationale

3.1 Introduction

The dependence of tumor growth and metastasis on angiogenesis has been well characterized and has led to exploration of the role of anti-angiogenic drugs (both small molecules and monoclonal antibodies) in the treatment of solid tumors. Such agents have shown promise in both animal models and in preliminary studies of solid carcinomas in humans– including SCLC and non-SCLC [1,2]. Among these studies, three sets of investigators have performed preliminary evaluations of thalidomide (an anti-angiogenic drug in the IMiD class) in combination with conventional induction chemotherapy and/or as mono-therapeutic, post-induction maintenance therapy in subjects with newly diagnosed SCLC [3,4,5]. In each of these studies, some benefit with thalidomide use was detected – an increase in median survival (about 3 months overall) and/or 1- and 2-year survival relative to either parallel administration of or historic institutional control using equivalent conventional induction chemotherapy alone.

Recently, the relative roles of enhanced expression/production of the inflammatory cytokines, including both cyclooxygenase-2 (COX-2) and tumor necrosis factor-alpha (TNF-alpha), in the up-regulation of lung cancer growth, the stimulation of metastasis, the inhibition of apoptosis and in the occurrence of paraneoplastic syndromes have been identified and investigated [6,7,8]. As a result of *in vitro* and *in vivo* studies on lung and other carcinomas, inhibition of TNF-alpha and COX-2 have been identified, along with inhibition of angiogenesis, as therapeutic targets for limiting the growth, metastasis and neuro-endocrine complications of various solid carcinomas.

The emergence of immunomodulatory agents, such as thalidomide, lenalidomide and more recently CC-4047 (pomalidomide), as effective therapies has altered the therapeutic paradigm for multiple myeloma (MM). Following the approval and establishment of thalidomide-containing regimens, such as melphalan, prednisone and thalidomide (MPT) and Thal/Dex, as the standard first-line therapy for newly diagnosed MM (NDMM), lenalidomide in combination with standard high-dose dexamethasone (RD) was approved for the treatment of subjects with previously treated MM. However, even with the newly approved agents including thalidomide, lenalidomide and proteasome inhibitor such as bortezomide, MM remains an incurable disease and most subjects will eventually relapse and progress after multiple lines of different therapeutic regimens.

In addition, thalidomide, especially when combined with a corticosteroid, is effective in other diseases related to AL-amyloid including Waldentroms macroglobulinemia, Castleman disease and POEMS (polyneuritis, organomegaly, endocrinopathy, M-protein and osteosclerosis) syndrome. Substantial data indicate thalidomide combined with a corticosteroid with or without an alkylating drug is active in newly-diagnosed and progressive AL-amyloidosis with responses rates of 20-75 percent. Preliminary data indicate lenalidomide and corticosteroids are active in AL-amyloidosis including subjects failing melphalan (at all doses) and corticosteroids and also thalidomide and corticosteroids.

3.2 Pomalidomide

Pomalidomide, a thalidomide analogue, is an immune-modulatory agent that, among other anti-tumor properties, on an equimolar basis *in vitro*, displays equivalent anti-angiogenic activity, about 8-fold greater activity in stimulation of apoptosis, at least 10-fold greater activity in inhibition of cellular COX-2 production and over 4,000-fold greater activity in inhibition of cellular TNF-alpha production relative to thalidomide [9,10]. Pomalidomide has also been shown to stimulate antibody-dependent cytotoxic T-cell activity (ADCC) [9].

At tolerated doses (MTD = 2 mg QD and 5 mg QOD), pomalidomide has been shown to be active in subjects with relapsed or refractory multiple myeloma (MM) (study CC-4047-00-001) [9,11,12]. In 45 subjects who received doses of pomalidomide ranging, by cohort, up to 10 mg daily, the most commonly occurring dose-limiting toxicity (DLT) was reversible neutropenia. As with other IMiDs administered to subjects receiving concomitant systemic steroids, deep vein thrombosis (DVT) was seen (in 1subject each in this study and in its subsequent named subject supply rollover program) [9,13].

Pomalidomide has been studied in AL amyloidosis at the Mayo clinic. Thirty-one subjects with previously-treated AL amyloidosis are enrolled and the data on 29 evaluable subjects were presented at ASH meeting in December 2010. Overall hematologic response rate is 38% with 8 subjects achieving PR and 3 VGPR, including subjects failing prior lenalidomide and/or thalidomide. One year overall and progression free survival are 77% and 56% respectively. Twenty one of 29 subjects experienced \geq grade -3 AEs possibly attributed to treatment. The conclusions were that pomalidomide could provide a safe and effective therapy in previously treated subjects with AL amyloidosis, including those failing lenalidomide and/or thalidomide.

Complete and updated adverse events are available in the Investigational Drug Brochure and the IND Safety Letters.

